11.5.3 Exploratory Endpoints

For the exploratory endpoints listed below, unless otherwise noted, the Chi-squared test will be used for categorical endpoints, the t-test for continuous endpoints, and Log-rank test for time-to-event endpoints. In comparison of means, the Satterthwaite t-test may be used when variances between the two groups are different. These tests will evaluate etanercept monotherapy vs methotrexate monotherapy and etanercept and methotrexate combination therapy vs methotrexate monotherapy.

Components of SDAI at all measured timepoints

The five components of SDAI will be summarized as observed with descriptive statistics by treatment arm for the PAS.

HAQ-DI at all measured timepoints

HAQ-DI will be summarized with descriptive statistics as observed by treatment arm for the PAS.

SF-36 domains, physical component summary, and mental component summary at all measured timepoints

SF-36 domains will be summarized with descriptive statistics as observed by treatment arm for the PAS.

SDAI score at run-in visits

SDAI score at Run-In Visit 1, Run-In Visit 2, and Run-In Visit 3 will be summarized with descriptive statistics as observed for the FAS. No statistical tests will be performed.

Time to run-in failure

Kaplan-Meier curves will assess time to run-in failure for the FAS. Subjects who do not experience run-in failure are censored at their end of run-in date, where reason is not stated as protocol specified criteria or ineligibility determined due to failing to meet Part 2 Inclusion Criteria (116) or due to fulfilling Part 2 Exclusion Criteria (228) per Section 4.2.1 and 4.2.2, respectively, in the protocol.

Time to Randomization Failure

Kaplan-Meier curves will assess time to randomization failure for the FAS. Subjects who are randomized are censored at their end of run-in date.

Product: Etanercept
Statistical Analysis Plan: 20110186
Dated: 7 January 2020

Page 37

Patient Global Assessment of Joint Pain at all measured timepoints

Patient Global Assessment of Joint Pain will be summarized with descriptive statistics as observed by treatment arm for the PAS.

Observed SDAI remission at all measured timepoints

Observed SDAI remission at each analysis visit will be summarized for the Primary Analysis Set, where observed SDAI remission is defined in [Section 6.5](#).

Observed SDAI remission at visits following rescue

Observed SDAI remission by Rescue_Visit and by DW_Visit will be summarized for the Rescue Analysis Set and the Disease-Worsening Analysis Set, respectively, where Rescue_Visit and DW_Visit are defined in [Appendix A](#).

SDAI LDA, DAS28-ESR LDA at all measured timepoints, SDAI LDA, DAS28-ESR LDA at visits following rescue

The observed proportion of subjects achieving SDAI LDA and DAS28-ESR LDA will be tabulated at each Analysis Visit for the PAS. A similar analysis will be done for the Rescue Analysis Set and the Disease-Worsening Analysis Set by Rescue_Visit and DW_visit, respectively.

DAS28-ESR remission and DAS28-CRP remission at all measured timepoints,
DAS28-ESR remission and DAS28-CRP remission at visits following rescue

The observed proportion of subjects achieving DAS28-ESR remission and DAS28-CRP remission will be tabulated at each Analysis Visit for the PAS. A similar analysis will be done for the Rescue Analysis Set and the Disease-Worsening Analysis Set by Rescue_Visit and DW_visit, respectively.

Reason for Disease-Worsening (DW)

Reason for Disease-Worsening (DW) will be summarized by Analysis Visit for the Disease-Worsening Analysis Set. If a subject's visit results in fulfillment of more than one of these criteria, only a single reason for disease-worsening will be counted, with priority given in the following order:

Priority 1: SDAI > 11

Priority 2: SDAI > 3.3 and ≤ 11 on two consecutive visits at least two weeks apart

Priority 3: SDAI > 3.3 and ≤ 11 on three or more separate visits

No statistical tests will be performed.

SDAI score at Disease-Worsening and at visits following rescue; Change in SDAI from Disease-Worsening Date at visits following rescue

SDAI score at Disease-Worsening Date and by DW_Visit will be summarized with descriptive statistics by treatment arm for the Disease-Worsening Analysis Set. A similar analysis will be done for Change in SDAI from Disease-Worsening Date by DW_Visit. Similar analyses will be performed for the Rescue Analysis Set by Rescue Visit. The latest SDAI score on or prior to a subject's rescue date is used as their Rescue Baseline SDAI value.

Disease Activity at Disease-Worsening

The magnitude of disease activity as measured by the SDAI score at Disease-Worsening Date will be summarized per the definition in [Section 6.5](#) for the Disease-Worsening Analysis Set. Chi-squared tests will evaluate etanercept monotherapy vs methotrexate monotherapy and etanercept and methotrexate combination therapy vs methotrexate monotherapy.

Time to SDAI LDA, Time to DAS28-ESR Remission, Time to DAS28-CRP Remission

Time to SDAI LDA, time to DAS28-ESR remission, time to DAS28-CRP remission will be evaluated with Kaplan Meier curves and Log-rank tests for the Rescue Analysis Set and the Disease-Worsening Analysis Set.

Table 2. Exploratory Endpoints Summary Table

Endpoint	Primary Summary and Analysis Method	Exploratory Analysis
Exploratory Endpoints		
Components of SDAI at all measured timepoints	Summary statistics for the components of SDAI at each Analysis Visit for the PAS. T-test comparing etanercept monotherapy vs methotrexate monotherapy T-test comparing etanercept and methotrexate combination therapy vs methotrexate monotherapy	
HAQ-DI at all measured timepoints	Summary statistics for the components of HAQ-DI at each Analysis Visit for the PAS. T-test comparing etanercept monotherapy vs methotrexate monotherapy T-test comparing etanercept and methotrexate combination therapy vs methotrexate monotherapy	

Table 2. Exploratory Endpoints Summary Table

Endpoint	Primary Summary and Analysis Method	Exploratory Analysis
Exploratory Endpoints(Continued)		
SF-36 domains, physical component summary, and mental component summary at all measured timepoints	Summary statistics for SF-36 domains at each Analysis Visit for the PAS. T-test comparing etanercept monotherapy vs methotrexate monotherapy T-test comparing etanercept and methotrexate combination therapy vs methotrexate monotherapy	
SDAI score at run-in visits	Summary statistics for SDAI for the FAS. A scatter plot for each subject's SDAI score at Run-in Visits 1, 2, and 3.	
Time to run-in failure	Kaplan-Meier curves assessing Time to run-in failure for the FAS. Subjects who do not experience run-in failure are censored at their End of Run-In date.	
Time to Randomization Failure	Kaplan-Meier curves assessing Time to end of run-in for the FAS. Subjects who are randomized are censored at End of Run-In Date.	
Observed SDAI Remission (≤ 3.3) at all timepoints	Similar analysis as SDAI remission at all measured timepoints for the PAS. See definition of Observed SDAI Remission in Section 6.5 .	
Patient Global Assessment of Joint Pain at all timepoints	Summary statistics for PtGAJP at each Analysis Visit for the PAS. T-test comparing etanercept monotherapy vs methotrexate monotherapy T-test comparing etanercept and methotrexate combination therapy vs methotrexate monotherapy	
SDAI LDA at all timepoints	Similar analysis as SDAI remission at all measured timepoints for the PAS.	
DAS28-ESR remission at all timepoints	Similar analysis as SDAI remission at all measured timepoints for the PAS.	
DAS28-ESR LDA at all timepoints	Similar analysis as SDAI remission at all measured timepoints for the PAS.	
DAS28-CRP remission at all timepoints	Similar analysis as SDAI remission at all measured timepoints for the PAS.	
Reason for Disease-Worsening	Observed count (percentage) of reason for disease-worsening at each Analysis Visit for the Disease-Worsening Analysis Set.	

Table 2. Exploratory Endpoints Summary Table

Endpoint	Primary Summary and Analysis Method	Exploratory Analysis
Exploratory Endpoints(Continued)		
SDAI score at Disease-Worsening	Summary statistics for the SDAI score at DW Date for the Disease-Worsening Analysis Set. T-test comparing etanercept monotherapy vs methotrexate monotherapy T-test comparing etanercept and methotrexate combination therapy vs methotrexate monotherapy	
Disease Activity at Disease-Worsening	Observed count (percentage) of subjects in each Disease Activity category (Low, Moderate, High) at DW Date for the Disease-Worsening Analysis Set. Chi-squared test comparing etanercept monotherapy vs methotrexate monotherapy Chi-squared test comparing etanercept and methotrexate combination therapy vs methotrexate monotherapy	
Observed SDAI remission at visits following rescue	Observed count (percentage) of subjects achieving observed SDAI remission by Rescue_Visit for the Rescue Analysis Set. Chi-squared test comparing etanercept monotherapy vs methotrexate monotherapy Chi-squared test comparing etanercept and methotrexate combination therapy vs methotrexate monotherapy	Similar to the Primary Analysis Method but using the Disease-Worsening Analysis Set and DW_Visit.
SDAI LDA at visits following rescue	Similar analysis as for SDAI remission at visits following rescue	Similar to the Primary Analysis Method but using the Disease-Worsening Analysis Set.
Time to SDAI LDA	Similar analysis as Time to recapture SDAI remission after starting rescue treatment.	Similar analysis as the Primary Analysis Method but using the Disease-Worsening Analysis Set, looking at time to SDAI LDA from DW Date.

Table 2. Exploratory Endpoints Summary Table

Endpoint	Primary Summary and Analysis Method	Exploratory Analysis
Exploratory Endpoints(Continued)		
SDAI score on Disease-Worsening Date and at visits following rescue	Summary statistics for SDAI by Rescue_Visit for the Rescue Analysis Set. T-test comparing etanercept monotherapy vs methotrexate monotherapy T-test comparing etanercept and methotrexate combination therapy vs methotrexate monotherapy	Similar to the Primary Analysis Method but using the Disease-Worsening Analysis Set and DW_Visit.
Change in SDAI from Disease-Worsening Date and at visits following rescue	Similar analysis as for SDAI score on Disease-Worsening Date and at visits following rescue	Similar to the Primary Analysis Method but using the Disease-Worsening Analysis Set and DW_Visit.
DAS28-ESR remission at visits following rescue	Similar analysis as for SDAI remission at visits following rescue	Similar to the Primary Analysis Method but using the Disease-Worsening Analysis Set and DW_visit.
Time to DAS28-ESR remission	Kaplan-Meier curves assessing Time to DAS28-ESR remission from Rescue Date for the Rescue Analysis Set. Subjects with more than one event of DAS28-ESR remission will be analyzed using their first event date. Subjects who do not have DAS28-ESR remission are censored at their last SDAI assessment date. Log-rank test comparing etanercept monotherapy versus methotrexate monotherapy.	Similar to the Primary Analysis Method but using the Disease-Worsening Analysis Set, from DW Date.
DAS28-ESR LDA(yes/no) at visits following rescue	Similar analysis as for SDAI remission at visits following rescue	Similar to the Primary Analysis Method but using the Disease-Worsening Analysis Set and DW_Visit.
DAS28-CRP remission (yes/no) at visits following rescue	Similar analysis as for SDAI remission at visits following rescue	Similar to the Primary Analysis Method but using the Disease-Worsening Analysis Set and DW_Visit.
Time to DAS28-CRP remission	Similar analysis as Time to DAS28-ESR remission	Similar to the Primary Analysis Method but using the Disease-Worsening Analysis Set, from DW Date.

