6.4 Derived Variables

Duration of Rheumatoid Arthritis

The number of years between the date of diagnosis (DXDT) and Run-in Day 1, rounded to one decimal place, is given by formula below to calculate the duration:

Observed portion	Missing portion	Formula to Calculate Duration
Year, Month, Day		$(\text{Run-in Day 1} - \text{DXDT} + 1)/365.25$
Year, Month	Day	$[\text{Year}(\text{Run-in Day 1}) - \text{Year}(\text{DXDT})] + [\text{Month}(\text{Run-in Day 1}) - \text{Month}(\text{DXDT})]/12$ *if duration equals 0, add 1 month or 1/12 years (to avoid a disease duration of 0)
Year	Month, Day	$[\text{Year}(\text{Run-in Day 1}) - \text{Year}(\text{DXDT})]$ *if duration equals 0, add 1 month or 1/12 years (to avoid a disease duration of 0)

Time to Disease-Worsening

Time to Disease-Worsening = DW Date – Study Day 1 + 1

The subjects without Disease-Worsening will be censored at their last SDAI assessment date.

Only time to subject's *first* instance of disease-worsening will be evaluated.

Time-to-Event (for Rescue Analysis Set)

Time-to-Event = Earliest Date of Achievement of Event of Interest During the Rescue Therapy Period – Rescue Date + 1

For example, for subjects who recapture SDAI remission:

Time-to-Recapture SDAI remission = Earliest Date of Achievement of Observed SDAI remission During the Rescue Therapy Period – Rescue Date + 1

The subjects who do not experience the event of interest will be censored at their last SDAI assessment date.

Only time to subject's *first* instance of each event of interest will be evaluated.

Time-to-Event (for Disease-Worsening Analysis Set)

Time-to-Event = Earliest Date of Achievement of Event of Interest After
Disease-Worsening – DW Date + 1

For example, for subjects who recapture SDAI remission:

Time-to-Recapture SDAI remission = Earliest Date of Achievement of Observed SDAI
remission After Disease-Worsening – DW Date + 1

The subjects who do not experience the event of interest will be censored at their last SDAI assessment date.

Only time to subject's *first* instance of each event of interest will be evaluated.

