7.3 Disease-Worsening Analysis Set

The Disease-Worsening Analysis Set includes randomized subjects who meet the definition of Disease-Worsening at any point after randomization.

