7.4 Rescue Analysis Set

This includes randomized subjects who meet the definition of Disease-Worsening and have received both at least one dose of active rescue therapy etanercept and at least one dose active rescue therapy methoxrexate as recorded in the eCRF.

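### Time to DAS28-ESR and DAS28-CRP remission after rescue or worsening has no at-risk condition, so a subject who never left DAS28 remission counts as an event

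*SAP*

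**What the plan says.** **Analysis.** SAP Section 11.5.3 states: "Time to SDAI LDA, time to DAS28-ESR remission, time to DAS28-CRP remission will be evaluated with Kaplan Meier curves and Log-rank tests", for both the Rescue and the Disease-Worsening Analysis Sets. Table 2 describes the first of the DAS28 endpoints as "Kaplan-Meier curves assessing Time to DAS28-ESR remission from Rescue Date for the Rescue Analysis Set", using the first event date, and the DAS28-CRP row reads "Similar analysis as Time to DAS28-ESR remission".

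**Entry.** Section 7.4 defines the Rescue set: "This includes randomized subjects who meet the definition of Disease-Worsening and have received both at least one dose of active rescue therapy etanercept", and adds at least one dose of active rescue methotrexate. Section 7.3 reads: "The Disease-Worsening Analysis Set includes randomized subjects who meet the definition of Disease-Worsening at any point after randomization". Worsening (Section 6.5) is purely SDAI-based: above 3.3 and up to 11 on two consecutive visits at least two weeks apart, the same range on three or more visits, or any value above 11.

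**Event and clock.** Section 6.5 defines DAS28-ESR and DAS28-CRP remission as a value below 2.6 at the timepoint in question. Section 6.4 takes, for the Rescue set, "Earliest Date of Achievement of Event of Interest During the Rescue Therapy Period", subtracts the Rescue Date and adds 1. For the Disease-Worsening set it takes the earliest qualifying date after worsening and counts from the DW Date. Section 6.1 starts the Rescue Therapy Period on the Rescue Date itself.

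None of Sections 6.4, 7.3, 7.4 or 11.5.3, nor Table 2, sets a condition on DAS28 at time zero or handles subjects already below 2.6.

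**The concern.** A time-to-event curve is meaningful when everyone at time zero is still able to have the event. For SDAI remission the entry rule secures this, because worsening requires SDAI above 3.3. For DAS28 remission nothing does so. Protocol Section 2.4 itself describes SDAI remission as the stricter standard, so losing it does not imply losing DAS28 remission.

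A subject whose DAS28 stayed below 2.6 throughout would be recorded as reaching DAS28 remission. On the Rescue Date this would happen before rescue could have acted.

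SAP Section 12 says the added endpoints are meant to show, among other things, how far subjects improve after rescue even without regaining SDAI remission. A subject already under the threshold cannot show improvement to it. Two things are at stake: how the post-rescue curves read, and whether the between-arm log-rank tests are confounded by DAS28 status at entry.

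**Working it through.** The plan states no figure for these endpoints, so there is none to reproduce. The check has three steps.

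**1. Can SDAI worsening coexist with DAS28 below 2.6?** The formulas are from SAP Appendix A (TJC and SJC are the 28-joint tender and swollen counts; globals in mm):

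- SDAI = TJC + SJC + PtGA/10 + PhGA/10 + CRP (mg/dL)
- DAS28-ESR = 0.56√TJC + 0.28√SJC + 0.70 ln(ESR) + 0.014 PtGA
- DAS28-CRP = 0.56√TJC + 0.28√SJC + 0.36 ln(CRP in mg/L + 1) + 0.014 PtGA + 0.96

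Worked example: no tender or swollen joints, PtGA 25, PhGA 15, CRP 3 mg/L (0.3 mg/dL), ESR 10.

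- SDAI = 2.5 + 1.5 + 0.3 = 4.3
- DAS28-ESR = 0.70 × 2.303 + 0.35 = 1.96
- DAS28-CRP = 0.36 × 1.386 + 0.35 + 0.96 = 1.81

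Other illustrative profiles:

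| TJC | SJC | PtGA | PhGA | CRP mg/L | ESR | SDAI | DAS28-ESR | DAS28-CRP |
|---|---|---|---|---|---|---|---|---|
| 1 | 1 | 10 | 10 | 3 | 10 | 4.3 | 2.59 | 2.44 |
| 0 | 2 | 20 | 10 | 4 | 12 | 5.4 | 2.42 | 2.22 |
| 0 | 5 | 20 | 30 | 3 | 8 | 10.3 | 2.36 | 2.37 |
| 0 | 8 | 10 | 25 | 3 | 8 | 11.8 | 2.39 | 2.39 |
| 2 | 2 | 30 | 30 | 5 | 15 | 10.5 | 3.50 | 3.21 |

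The first four are below 2.6 on both scores; the last is not. The overlap arises because neither DAS28 formula uses the physician global, and swollen joints enter only as 0.28 times a square root.

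An unweighted grid was also run: joint counts 0 to 5, globals 0 to 50 mm, CRP 0.1 to 1.0 mg/dL, ESR 5 to 20. Of points with SDAI above 3.3 and up to 11, about 34% had DAS28-CRP below 2.6 and about 28% had DAS28-ESR below 2.6. Above SDAI 11 both were about 3%. This shows that the overlap is feasible and sits mainly in low-activity worsening. It is not a prevalence estimate.

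**2. Effect on the curves.** Let f be the share below 2.6 at time zero and p the share of the others who truly reach remission by the first later visit. In the Rescue set, with DAS28 measured on the Rescue Date, the event proportion by that visit is f + (1 − f)p. With the restriction it is p.

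| f (assumed) | p = 0.30 | p = 0.50 |
|---|---|---|
| 0 | 0.30 | 0.50 |
| 0.2 | 0.44 | 0.60 |
| 0.4 | 0.58 | 0.70 |
| 0.6 | 0.72 | 0.80 |

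For example, 0.4 + 0.6 × 0.50 = 0.70. In the Disease-Worsening set a later value is needed. If a share s of those starting below 2.6 are still below at the first later visit, the proportion is fs + (1 − f)p. This exceeds p whenever s is greater than p.

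**3. Effect on the log-rank test.** True recapture was simulated as equal in both arms: 0.4 per visit over three visits, 2,000 runs, subjects already below 2.6 counted at day 1. Arm sizes of 28 and 50 were assumed; they equal the planning non-response, 100 × (1 − 0.72) and 100 × (1 − 0.50).

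| f, arm of 28 | f, arm of 50 | Rejection at nominal 5% |
|---|---|---|
| 0 | 0 | 4.8% |
| 0.3 | 0.3 | 4.3% |
| 0.4 | 0.3 | about 11% |
| 0.5 | 0.3 | 24% |
| 0.6 | 0.3 | 47% |

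With equal f the error rate stays near 5%. It rises only when f differs between arms.

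**The case against.** Several stronger readings are tempting, and the documents do not support them.

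- *Non-flares are counted as events.* Every subject in both sets met the trial's own worsening definition, so all flared on SDAI. What some may not have lost is DAS28 remission.
- *Many subjects are affected.* No document gives the share. Hand-picked profiles and an unweighted grid show possibility only, and one profile is marginal: DAS28-ESR 2.59 at ESR 10 becomes 2.66 at ESR 11.
- *The arms differ in their mix of low-activity and SDAI > 11 worsening, so the log-rank tests reflect that mix.* The documents give no mix by arm. The bias is conditional on a difference.
- *The by-visit DAS28 remission proportions are also invalid.* They describe a state at each visit and need no prior loss of remission.

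Other defences carry some weight. The SAP uses the word recapture for SDAI remission and calls the DAS28 endpoints simply time to remission, so it makes no explicit claim that DAS28 remission had been lost. It also summarizes disease activity, SDAI score and reason at worsening, so an imbalance in severity would be partly visible; but those summaries are SDAI-based and do not show DAS28 status at entry. Because both sets are selected after randomization, even a restricted log-rank test would not isolate the effect of rescue. The day-1 event follows from the text only in the Rescue set.

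None of this supplies the missing at-risk condition.

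**Conclusion.** The point holds as a limited one. As written, the two DAS28 time-to-remission analyses count as events subjects who had no DAS28 remission to regain. The Rescue-set event proportion is too high whenever any such subject is present (f above 0, p below 1). The Disease-Worsening set is affected in the same direction if those already in remission stay there more often than the others reach it. At p = 0.50, the overstatement by the first visit in the Rescue set is 10 to 30 percentage points for f between 0.2 and 0.6. The log-rank comparison is biased only if f differs between arms. The values of f and p are assumptions, because the documents give neither.

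Time to SDAI LDA has the same fault with more certainty. Section 6.5 defines LDA as SDAI above 3.3 and up to 11, so a subject who worsens through either low-activity criterion already meets it on the DW Date.

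All these endpoints are exploratory. The primary and secondary conclusions do not depend on them.

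**What to change.** In SAP Section 11.5.3 and the corresponding Table 2 rows:

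1. Restrict time to DAS28-ESR remission to subjects with DAS28-ESR of 2.6 or higher at the Rescue or Disease-Worsening baseline, and likewise for DAS28-CRP with its own score.
2. Count only assessments after that baseline, so that a rescue-day value cannot be both baseline and event.
3. Report by arm how many subjects were already below 2.6.
4. Apply the same at-risk condition to time to SDAI LDA, that is, SDAI above 11 at baseline.
5. Keep the by-visit DAS28 remission proportions on the whole set, with baseline DAS28 status shown alongside.

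The cost is SAP wording and smaller denominators for these exploratory curves. No new data are needed: Protocol Table 1 schedules the joint counts, patient global, ESR and CRP at every double-blind visit and at Disease Assessment visits.

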#### **7.4.2 Erythrocyte Sedimentation Rate**

ESR will be performed locally at each site and the ESR data will be submitted to the central laboratory per the instructions in the study manual provided by the central laboratory. The central laboratory will provide all supplies. The screening and baseline ESR may be performed by any trained staff at the site. Once the subject has been randomized, the ESR may only be performed by a trained individual at the site who does not perform any study assessments with subjects on the study. Staff performing the ESR must be identified on the delegation of authority for this responsibility. The results of the ESR performed after the subject has been randomized must be maintained in a blinded fashion so that it may not be viewed by staff who perform any study assessments with the subjects.

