6.1 Study Time Points

Enrollment Date

A subject's Enrollment Date is defined as the date he or she has met all Part 1 eligibility criteria and the enrollment call in the IXRS system has been completed.

Part 1/Run-in Period

The 24-week period after enrollment and prior to randomization. Specifically, the period begins when a subject initiates treatment with open-label run-in etanercept and/or open-label run-in methotrexate per the eCRF at the same dose he or she was receiving at screening. There are three visits associated with the Run-in Period: Run-in Visit 1, Run-in Visit 2, and Run-in Visit 3.

Run-In Day 1

A subject's Run-In Day 1 is defined as the date of the first dose of IP administration during Part 1.

Run-In Day

A subject's Run-In Day = (Visit Date – Run-In Day 1 date) + 1.

Run-In Failure Date

A subject's Run-In Failure Date is the date the subject ended run-in due to protocol specified criteria per the eCRF.

Randomization Failure Date

A subject's Randomization Failure Date is the date the subject ended run-in due to any reason and was not randomized.

End-of Run-In Date

A subject's End-of Run-In Date is the date subject ends the run-in period per the CRF.

Randomization Date

A subject's Randomization Date is the date when a randomization number is assigned to him or her through the Interactive Voice/Web Response System (IXRS).

Study Day 1

A subject's Study Day 1 is defined as the date of the first dose of IP administration after randomization, or the randomization date if the subject is not dosed.

Baseline

The last measurement for the endpoint of interest taken on or prior to Study Day 1 and after Run-In Visit 3. Hematology and chemistry profiles were not assessed on Day 1; their Run-in Visit 3 values will be used when reporting baseline.

Baseline for Concomitant Medications

Run-In Period Baseline for Concomitant Medications is enrollment date, and Post-Run-In Period Baseline for Concomitant Medications is randomization date.

Study Day

For a given study visit, the study day for a subject is defined as:

Study Day = (Visit Date – Study Day 1 date) + 1.

Part 2/Treatment Period

The up-to 48-week double-blind period beginning with Study Day 1 and ending with the End of Study date.

SDAI Assessment Datea

The SDAI Assessment Date is the latest date of the assessments for Tender Joint Count, Swollen Joint Count, Physician Global Assessment, Patient Global Assessment, and CRP for a given SDAI score.

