6.5 Study Endpoints

Patient Global Assessment of Joint Pain (PtGAJP)

An assessment of the severity of the subject's joint pain (0=no pain at all, 100=worst pain imaginable) completed by the patient using a visual analog scale (VAS) in mm.

Patient Global Assessment of Disease Activity (PtGA)

A global assessment of the subject's arthritis (0=no arthritis activity at all, 100=worst arthritis activity imaginable) completed by the patient using a visual analog scale (VAS).

Physician Global Assessment of Disease Activity (PhGA)

A global assessment of the subject's arthritis (0=no activity at all, 100=worst activity imaginable) completed by the physician using a visual analog scale (VAS).

Swollen Joint Count

A score that assesses the presence or absence of swelling in 66 joints. There are also a 28-joint Swollen Joint Count and a 28-joint Plus Feet and Ankles Swollen Joint Count. Details of the scoring algorithm are described in [Appendix A](#).

Tender Joint Count

A score that assesses the presence or absence of tenderness in 68 joints. There are also a 28-joint Tender Joint Count and a 28-joint Plus Feet and Ankles Tender Joint Count. Details of the scoring algorithm are described in [Appendix A](#).

Simplified Disease Activity Index (SDAI)

A composite score that is based on the number of tender and swollen joints using a 28-joint count, PhGA (0-10 visual analog scale), PtGA (0-10 visual analog scale), and CRP in mg/dL. A higher score represents worse disease.

Details of the scoring algorithm are described in [Appendix A](#).

SDAI Remission at Analysis Visit k

For Analysis Visits other than Week 48, SDAI Remission at a given Visit will be derived using the same approach as in [Section 6.2](#), replacing Week 48 with the Analysis Visit Week k , and replacing “subject did not fulfill the definition of disease-worsening during the study” with “subject did not *previously* fulfill the definition of disease-worsening”.

Specifically,

- SDAI_remission_maintenance (≤ 3.3) at Week $k = 1$,
if SDAI ≤ 3.3 at Week k AND subject did not previously fulfill the definition of disease-worsening;
- SDAI_remission_maintenance (≤ 3.3) at Week $k = \text{missing}$,
if subject has no Week k SDAI value AND subject did not previously fulfill the definition of disease-worsening;
- SDAI_remission_maintenance (≤ 3.3) at Week $k = 0$,
otherwise.

Observed SDAI Remission at Analysis Visit k

- Observed_SDAI_Remission at Analysis Visit $k = 1$,

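### Time to DAS28-ESR and DAS28-CRP remission is censored at the last SDAI date rather than at the last date of the index that defines the event, which shifts the Kaplan-Meier estimates for these two exploratory endpoints

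*SAP*

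**What the plan says.** SAP Section 11.5.3, Table 2, defines time to DAS28-ESR remission from the rescue date in the Rescue Analysis Set and repeats it from the disease-worsening date in the Disease-Worsening Analysis Set. The event rule is "Subjects with more than one event of DAS28-ESR remission will be analyzed using their first event date" and the censoring rule is "Subjects who do not have DAS28-ESR remission are censored at their last SDAI assessment date". The DAS28-CRP row reads "Similar analysis as Time to DAS28-ESR remission". SAP 6.4 sets the same date for any event in either analysis set: "The subjects who do not experience the event of interest will be censored at their last SDAI assessment date".

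SAP 6.1 builds that date from the SDAI components: "The SDAI Assessment Date is the latest date of the assessments for Tender Joint Count, Swollen Joint Count, Physician Global Assessment, Patient Global Assessment", completed by CRP and tied to an existing score ("Patient Global Assessment, and CRP for a given SDAI score"). ESR is not among them. Neither document gives a censoring date specific to DAS28.

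**The concern.** A Kaplan-Meier estimate needs the date up to which each event-free subject is known to be event-free. For DAS28 remission that is the last date with a DAS28 value. The SDAI date can fall on either side of it.

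- **SDAI date later.** The subject stays in the risk set, counted as not in remission, at a visit where DAS28 could not be calculated. SAP 6.5 itself codes DAS28-ESR remission at such a visit as missing, not as 0. This pulls the estimated remission proportion down.
- **SDAI date earlier.** At a late visit with a DAS28 but no SDAI, a remission is counted as an event, while a non-remission adds no follow-up. Whether the visit counts depends on its result, which pushes the estimate up.

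At stake are the curves that describe how quickly subjects regain DAS28 remission after rescue or disease-worsening.

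**Working it through.** **Step 1. Which components each index needs.** From SAP 6.5 and Appendix A:

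| Index | 28-joint counts | Patient global | Physician global | CRP | ESR |
|---|---|---|---|---|---|
| SDAI | yes | yes | yes | yes | no |
| DAS28-ESR | yes | yes | no | no | yes |
| DAS28-CRP | yes | yes | no | yes | no |

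SAP 6.5 lists the last three SDAI inputs as "PhGA (0-10 visual analog scale), PtGA (0-10 visual analog scale), and CRP in mg/dL". SAP 10.3.3 does not impute missing components, so an index exists only when all of its components do.

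**Step 2. Where the indices can disagree.** The six components (tender count, swollen count, patient global, physician global, CRP, ESR) give 2^6 = 64 present/missing patterns:

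- SDAI present, DAS28-ESR missing: 1 pattern (ESR missing).
- SDAI present, DAS28-CRP missing: 0 patterns.
- SDAI missing, DAS28-ESR present: 3 patterns (physician global, CRP, or both missing).
- SDAI missing, DAS28-CRP present: 2 patterns (physician global missing, with or without ESR).

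ESR can be missing on its own. Protocol 7.4 sends CRP to the central laboratory, while ESR is done locally, and Protocol 7.4.2 says that after randomization "the ESR may only be performed by a trained individual at the site who does not perform any study assessments".

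**Step 3. Illustrative size.** The plan gives no figure to reproduce. All inputs here are assumed: three visits at 12, 24 and 36 weeks after rescue, first-remission hazards of 50%, 35% and 30%, remission that lasts once reached, and components missing independently at rate d per visit.

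- First remission at visit 1: 0.5. At visit 2: 0.5 × 0.35 = 0.175. At visit 3: 0.5 × 0.65 × 0.3 = 0.0975. Never: 0.5 × 0.65 × 0.7 = 0.2275.
- True 36-week remission: 1 − 0.2275 = 77.25%.

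*First effect (ESR missing, SDAI complete).* Under the SAP rule every non-event is censored at visit 3, so the estimate is the proportion with a detected event, 0.5(1 − d³) + 0.175(1 − d²) + 0.0975(1 − d):

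- d = 0.10: 0.4995 + 0.17325 + 0.08775 = 76.05%.
- d = 0.20: 0.496 + 0.168 + 0.078 = 74.20%.

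With censoring at the last DAS28-ESR, the events and numbers at risk per visit, as fractions of all subjects, give:

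- d = 0.10: 1 − (1 − 0.45/0.999)(1 − 0.2025/0.5445)(1 − 0.108/0.31275) = 77.40%.
- d = 0.20: 1 − (1 − 0.40/0.992)(1 − 0.22/0.576)(1 − 0.122/0.304) = 77.92%.

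The SAP rule is lower by 77.40 − 76.05 = 1.35 points and by 77.92 − 74.20 = 3.72 points.

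*Second effect (CRP missing at 10%, ESR complete).* All events are seen, but the never-remitters are censored at their last SDAI. The numbers at risk are 1 − 0.2275 × 0.1³ = 0.99977; 0.175 + 0.0975 + 0.2275 × (0.9 × 0.1 + 0.9) = 0.49773; and 0.0975 + 0.2275 × 0.9 = 0.30225. The estimate is 1 − (1 − 0.5/0.99977)(1 − 0.175/0.49773)(1 − 0.0975/0.30225) = 78.04%, which is 0.79 points above the 77.25% that own-index censoring gives.

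**Step 4. A different hazard.** A simulation of 400,000 subjects with a 40% chance of first remission per visit (true value 78.4%) gave the same directions:

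| Missing at 5% / 10% / 20% of visits | SAP rule | Own-index censoring |
|---|---|---|
| DAS28-ESR missing, SDAI complete | 77.7 / 76.6 / 74.2% | 78.5 / 78.5 / 79.0% |
| SDAI missing, DAS28 complete | 78.9 / 79.3 / 80.5% | 78.5 / 78.4 / 78.4% |

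**The case against.** **The mismatch may be rare.** Protocol Table 1 schedules ESR, CRP, joint counts and both globals at the same visits, and Protocol Section 7 asks for all procedures of a visit on one day. A wholly missed visit removes SDAI and DAS28 together and creates no mismatch; only an isolated missing component does. This stands. The documents give neither missingness rates nor remission hazards, and nothing in them supports a rate as high as 20%. At 5% ESR missing, the Step 3 formula gives 76.7% against a true 77.25%. Three scheduled visits after rescue also require rescue by about week 12.

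**A reader might infer that both effects apply to both endpoints.** They do not. Every DAS28-CRP component is an SDAI component, so a visit with an SDAI always has a DAS28-CRP. Only the second effect can reach that endpoint, through a missing physician global.

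**A reader might infer that any visit with a gap distorts the curve.** The two rules differ only at the end of follow-up. A gap followed by a later visit with both indices is carried as at risk under either rule.

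**A reader might infer that the log-rank tests are biased.** The documents do not support that. The same rule applies in every arm, original assignments stay blinded, and all rescued subjects receive the same combination. A two-arm simulation with the Step 3 hazards, equal missingness and assumed groups of 30 and 50 gave these type I errors at a nominal 5%, SAP rule against own-index rule: 4.9% and 4.9% (ESR 10% missing), 5.0% and 5.0% (ESR 20%), 5.4% and 5.5% (SDAI 10%). Power under one assumed alternative differed by less than 1 point. The comparison suffers if missingness differs by arm: with identical hazards, ESR complete in one arm and 20% missing in the other, the SAP rule gives 77.25 − 74.20 = 3.05 points of spurious difference.

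**Conclusion.** The censoring rule is wrong as written for two exploratory endpoints, because it takes follow-up from an index that does not define the event. For DAS28-ESR, late visits without ESR count as event-free. For both endpoints, late visits without SDAI count only when remission is found. This changes the level of the Kaplan-Meier estimates: about 1 to 4 points down for the first effect at 10% to 20% ESR missing, and under 1 point up for the second at 10% CRP missing. The directions follow from the definitions. The sizes rest on assumed missingness rates and assumed hazards, so they are illustrations and not forecasts. The log-rank comparison is materially affected only if missingness differs by arm, which the documents give no reason to expect. The primary and secondary endpoints do not use a DAS28 event time and are unaffected. This is a minor correction.

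**What to change.** In SAP Table 2 and SAP 6.4, for both the Rescue and the Disease-Worsening Analysis Sets:

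- Censor subjects without DAS28-ESR remission at their last non-missing DAS28-ESR assessment date.
- Censor subjects without DAS28-CRP remission at their last non-missing DAS28-CRP assessment date.
- Keep the SDAI assessment date for SDAI events only.

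The cost is a line of wording and one date variable in two exploratory analyses; no new data are needed. The change reduces the bias but does not remove it: at 20% ESR missing the own-index estimate in Step 3 is 77.92% against a true 77.25%, still 0.67 points high. Reporting by arm how many subjects have different last SDAI and last DAS28 dates would show whether the choice matters in the actual data.
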